3.1 Major protocol deviations

Deviations from the protocol will be registered as protocol deviations with classification:

- Major
- Minor

and category

- Informed consent
- Eligibility criteria

- Withdrawal criteria not adhered to
- Dosing deviation
- Visit window
- Missed procedure(s)
- Specimen deviation
- Unblinding
- Safety reporting
- Other

Before DBL and unblinding, all protocol deviations will be evaluated. Protocol deviations classified as major can lead to exclusion from PP analysis set. The decisions will be documented in the DBL minutes.

The following will be assessed as major protocol deviations:

- Violation of inclusion criteria 5, 6 or 7
- Receipt of any investigational TB vaccine previously (excl. crit. 10)
- Receipt of any new investigational drug or investigational vaccine from Visit 1 through Visit 8 (excl. crit. 11)
- Receipt of any licensed vaccine from Visit 1 through Visit 6 (excl. crit. 12) except for SARS-Cov-2 vaccines recommended by national vaccination programs, which will be allowed if given > 28 days before and from the time of administration of clinical trial product.
- Receipt of treatment likely to modify the immune response (e.g., blood products, immunoglobulins, immunosuppressive treatment) within 42 days before Visit 3 through Visit 6. Inhaled and topical corticosteroids are permitted (excl. crit. 13)
- Received TB treatment (Rifampicin, Isoniazid, Pyrazinamide or Ethambutol) for current episode for more than 28 weeks
- Received the second vaccine outside visit window. The window was extended to two months after day 56 during the Covid-19 pandemic.
- Did not receive the 2nd vaccination
- Did not receive treatment as randomised
- HIV+ detection between Visit 3, Day 0 and Visit 6, Day 70 (14 days after the 2nd vaccination)
- Other protocol deviations which are assessed as having a clinically or statistically significant effect

Protocol deviations leading to exclusion from the PP analysis set will be summarised by treatment and in total. Number and percentages of participants will be presented, and percentages will be based on all randomised participants. Covid-19 related protocol deviations will be summarised by treatment, classification, (major/minor), and category. A similar summary of all protocol deviations will be made. Protocol deviations are rated into major or minor in the eCRF.

All protocol deviations will be listed by participant.

4 Planned Statistical Methods

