- The participant is HIV tested (including CD4 count for participants who test HIV positive) and immunology samples are taken, see Table 3-2.
- If *Mtb* positive by culture in the study, the participant is informed of TB test results, referred to TB treatment management as per national programme guidelines (if not previously done), and is withdrawn (at the ET Visit) due to verified recurrent TB.
- If *Mtb* negative by culture in the study the participant is informed of TB test results, continues in the study and no ET Visit is completed.
- If *Mtb* negative by culture or the study culture result is pending, but the referral clinic diagnosed recurrent TB and started TB treatment, 2 additional sputum samples must be collected as soon as possible for repeat *Mtb* testing by culture, and the participant is withdrawn from the study.

Figure 2-1 Study Flow Diagram

Upon written approval of the Sponsors and relevant approvals for the Protocol Amendment v5.0, participants may be screened at a combined V1 and V2. This visit will be scheduled when the participant has completed at least 5 months (22 weeks) of TB treatment and TB treatment must be ongoing.

An internal data review committee, consisting of the coordinating principal investigator (PI), the site PIs and the medically responsible person from each of the co-sponsors, will convene during the study to review the blinded reported SAEs, AEs including AEs of special interest, injection site reactions and laboratory safety test results to identify any possible safety issues when:

- The first 150 participants across all sites have received their 1st vaccination and the 14 days safety follow-up data is available
- The first 150 participants across all sites have received their 2nd vaccination and the 14 days safety follow-up data is available

An independent data safety monitoring board (DSMB) will be established, consisting of a panel of independent experts, who will operate according to a DSMB charter. The DSMB will be convened if:

- A stopping rule is triggered
- The internal data review committee requests a DSMB meeting based on their review of the safety data

For more details on the internal data review committee review of safety data and the DSMB procedures, please see sections 5.1.4 and 6.2.

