3.2.4 Exclusion Criteria

Participants must meet none of the exclusion criteria at the time of randomization and vaccination:

1. Diagnosis or co-diagnosis of extra pulmonary TB.
2. Hospitalized for the current episode of drug-susceptible pulmonary TB disease.
3. History of receipt of treatment against active TB, prior to the current treatment episode, within the last 5 years.
4. History of or ongoing severe disease that in the opinion of the investigator might affect the safety of the participant or the immunogenicity of the investigational product.
5. Insulin dependent diabetes.

6. History of allergic disease or reactions likely to be exacerbated by any component of the investigational product.
7. History or laboratory evidence of immunodeficiency, autoimmune disease or immunosuppression.
8. History of chronic hepatitis.
9. Severe anemia, defined as hemoglobin less than 10 g/dL or a hematocrit less than 30 % based on most recent hematology obtained before randomization.
10. Receipt of any investigational TB vaccine previously.
11. Receipt or planned receipt of any investigational drug or investigational vaccine from V1 through V8= Day 421.
12. Receipt or planned receipt of any licensed vaccine from V1 through V6= Day 70, except for SARS-Cov-2 vaccines recommended by national vaccination programs which will be allowed if given > 28 days before and from the time of administration of clinical trial product.
13. Receipt of treatment likely to modify the immune response (e.g. blood products, immunoglobulins, immunosuppressive treatment) within 42 days before V3= Day 0 through V6= Day 70. Inhaled and topical corticosteroids are permitted.
14. Has a body mass index (BMI) < 13 (weight, kg / height, m²) on the date of V1.
15. Female participants of childbearing potential (not sterilized, menstruating or within 1 year of last menses, if post-menopausal): if not willing to use an acceptable method to avoid pregnancy (sterile sexual partner, sexual abstinence, hormonal contraceptives (oral, injection, transdermal patch, or implant) or intrauterine device from 28 days before V3= Day 0 until 2 months after the 2nd vaccination.
16. Female participants: if lactating / nursing, or pregnant as per positive pregnancy test on V2.
17. Not suitable for inclusion in the opinion of the investigator.

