- Per protocol (PP) analysis set: The PP analysis set will consist of all participants who received both doses of H56:IC31 or placebo within the specified dose intervals, who entered the evaluation period for efficacy 14 days after receipt of the 2nd dose of H56:IC31 or placebo with no HIV seroconversion, and who had no major protocol deviation of clinical or statistical significance. Major protocol deviations are defined in Section 3.1. Participants will be evaluated according to vaccination actually received.
- ITT analysis set: The ITT analysis set will consist of all randomised participants. Participants will be evaluated as randomised.
- Immunogenicity analysis set: The immunogenicity analysis set will consist of participants from the mITT population who received both doses of H56:IC31 or placebo and who are included in the immunogenicity cohort. Participants will be evaluated as randomised.

Clarifications to the protocol definitions are below in *italic*:

- *Participants with a recurrence of TB exactly on day 14 after 2nd dose are excluded from the mITT and PP analysis set.*
- *Participants who only received 1st vaccination will be excluded from the mITT if they experience a TB recurrence before Visit 6 when the visit is in the visit window, i.e., on day 67-73, or else before day 70.*
- *Efficacy endpoints are presented in section 6 and safety endpoints in section 7*

The classification of the participants will be performed before database lock (DBL).

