6.1 Time-to-event analyses

Time-to-event analyses will have start- and end-timepoint depending on the endpoint and analysis set as described in Table 1 and Table 2 below:

Table 1: Start-timepoints in time-to-event analyses

Endpoints	Population	Start-timepoint (Day=0)
All	All	Excluded from analysis if withdrawal or event before the day of the start-timepoint.
Primary endpoint (TB recurrence)	PP	Date of 2 nd vaccination + 14 days
Primary endpoint (TB recurrence) Secondary endpoint (TB disease relapse) Secondary endpoint (TB disease reinfection)	mITT	1. If received 2 nd vaccination then date of 2 nd vaccination + 14 except if withdrawn before 2. If missed 2 nd vaccination and visit 6 is within ± 3 days visit window (Day 67 to 73) then visit 6 3. Else Day 70 except if withdrawn before
1 st exploratory endpoint (TB recurrence or new TB treatment) 2 nd exploratory endpoint (TB recurrence - Xpert MTB/RIF Ultra or culture of sputum)	ITT	Date of 1 st vaccination
3 rd exploratory endpoint (TB recurrence)	mITT2	Date of 1 st vaccination + 30 except if withdrawn before

If TB event is not within the period between the start-timepoint and end-timepoint, then the participant will be censored as described in Table 2. Events on the day of the start time-point are included in the analyses with a time-to-event duration of 1 day.

Table 2: End-timepoints in time-to-event analyses

Endpoint	Population	End-timepoint
All	All	Completing the trial, terminating early or lost-to-follow-up without events are censored at the day of the last visit. End-timepoint is always on the day or after the start-timepoint.
Primary endpoint (TB recurrence)	PP mITT ITT	Event: 1. Date of sputum collection for culture-confirmed TB disease Censored: Earliest date of the following: 1. Date of last visit or TC, regardless of whether two sputum samples were collected 2. Date of sputum collection resulting in positive Xpert MTB/RIF Ultra (if followed by new TB treatment) for culture negative participants 3. Date of onset of new TB treatment, in the absence of any prior culture-confirmed TB disease recurrence

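### One listed deviation and one untimed item in SAP 3.1 can remove participants from the per-protocol set for something that happens after per-protocol follow-up has begun, so membership depends partly on the outcome

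*SAP*

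**What the plan says.** SAP section 3 limits the PP set to participants who had both doses within the dose interval, entered the efficacy period 14 days after dose 2 without HIV seroconversion, and "who had no major protocol deviation of clinical or statistical significance". In SAP 6.1, Table 1, PP follow-up starts at "Date of 2 nd vaccination + 14 days".

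SAP 3.1 lists the major deviations. One reads "Receipt of any new investigational drug or investigational vaccine from Visit 1 through Visit 8 (excl. crit. 11"). It takes over protocol exclusion criterion 11, "Receipt or planned receipt of any investigational drug or investigational vaccine from V1 through V8= Day 421". The licensed-vaccine, immune-modifying-treatment and HIV items end at Visit 6. The remaining specific items concern entry criteria, an earlier investigational TB vaccine, length of TB treatment, or dosing. The last item, "Other protocol deviations which are assessed as having a clinically or statistically significant effect", carries no time limit.

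On consequences, SAP 3.1 says "Protocol deviations classified as major can lead to exclusion from PP analysis set" and "Before DBL and unblinding, all protocol deviations will be evaluated". Table 2 gives three censoring reasons for the primary endpoint: last visit or call, a positive Xpert in a culture-negative participant followed by TB treatment, and start of new TB treatment. A protocol deviation is not among them.

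Protocol 2.2 says that a culture-positive participant is referred for treatment "and is withdrawn (at the ET Visit) due to verified recurrent TB". A participant whose referral clinic diagnoses recurrence and starts treatment is also withdrawn.

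**The concern.** An analysis set for a time-to-event comparison should be fixed by what is known when the clock starts. Here two items allow removal for something that happens later, and removal discards all of that participant's follow-up, including the valid time before the deviation.

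The chance of such removal depends on the outcome. A participant with recurrence on Day 150 is withdrawn and has little further time to acquire a deviation. A participant who stays event-free can acquire one until Day 421. Anyone excluded this way must still have been event-free at the moment of deviation, so the event-free time before it is lost selectively and PP incidence is pushed upward. If the arms deviate at different rates, VE moves too.

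SAP section 9 restarts the ITT analysis of the primary endpoint at Day 0. That leaves PP as the only supportive analysis set that shares the dose 2 + 14 days start with the mITT analysis of two-dose recipients. A comparison of mITT with PP is easier to read if PP carries no avoidable selection.

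**Working it through.** **Inputs from the documents** (protocol 7.5, SAP 2.2.1): placebo recurrence 4% per year, VE 60%, 450 per arm, 10% drop-out, 12 months of follow-up after Day 70, 20% two-sided type I error, 23 events, 80% power.

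**The plan's own figure.** Expected events are 450 × 0.90 × (0.04 + 0.016) = 16.2 + 6.48 = 22.68, or 23. At hazard ratio 0.40, the events required for 80% power are 21.5 (Schoenfeld) or 24.5 (Freedman). Power at 23 events is 82.0% or 78.0%. The figure reproduces, and the PP rule does not enter it.

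**Assumption.** The documents give no rate of post-Day-70 deviations that lead to exclusion. I use a constant annual rate q between 1% and 10%, and take every such deviation as leading to exclusion, which is the upper end of what the SAP permits.

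**Model.** There are 405 per arm (450 × 0.90), one year of follow-up and constant hazards:

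- Placebo λ = −ln(0.96) = 0.0408; vaccine λ = −ln(0.984) = 0.0161; true hazard ratio 0.395 (VE 60.5%).
- With m = λ + q, retained events per person are E = (λ/m)(1 − e^(−m)).
- Retained person-years under exclusion are P = λ[1 − e^(−m)(1 + m)]/m² + e^(−m), and the PP rate is E/P.
- If follow-up is instead censored at the deviation, person-years are (1 − e^(−m))/m and the rate returns to λ exactly.

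Worked case, placebo, q = 0.05: m = 0.0908, E = 0.0390, P = 0.9324, and the rate is 0.0390/0.9324 = 4.19 per 100 person-years against 4.08.

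**Equal deviation rates in both arms, with exclusion**

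| q per year | Placebo PP rate per 100 person-years | Hazard ratio | Excluded, placebo / vaccine | Later cases lost with them, placebo / vaccine |
|---|---|---|---|---|
| 0 | 4.08 | 0.395 | 0 / 0 | 0 / 0 |
| 1% | 4.10 | 0.395 | 3.9 / 4.0 | 0.08 / 0.03 |
| 2% | 4.12 | 0.395 | 7.9 / 8.0 | 0.16 / 0.06 |
| 5% | 4.19 | 0.395 | 19.4 / 19.6 | 0.40 / 0.16 |
| 10% | 4.29 | 0.395 | 37.8 / 38.2 | 0.78 / 0.31 |

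The relative rise is about q/2 (4.19/4.08 = 1.027 at 5%), because a deviation falls on average midway through the year and only the time before it is wrongly lost.

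**Deviations in one arm only, with exclusion**

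| q per year | Arm | Hazard ratio | VE |
|---|---|---|---|
| 5% | vaccine | 0.4051 | 59.5% |
| 5% | placebo | 0.3854 | 61.5% |
| 10% | vaccine | 0.4155 | 58.5% |
| 10% | placebo | 0.3758 | 62.4% |

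**Against sampling error.** The approximate standard error of the log hazard ratio is √(1/16.2 + 1/6.48) = 0.46. The one-arm 10% shift is ln(0.4155/0.3951) = 0.050, about a tenth of that (0.050/0.46 = 0.11).

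**The case against.** Much of the case on the other side stands.

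- **Breadth.** A reader might infer that any rule broken during follow-up costs a participant PP membership. The SAP does not say so. One listed item runs to Visit 8, and the open item reaches only deviations judged to have a clinically or statistically significant effect.
- **Certainty.** Exclusion is permitted, not automatic. Listing shell 16.2.2 records major status and PP exclusion separately, and its sample row shows a major deviation that does not exclude. Section 9 deliberately narrows the protocol wording on major deviations. Decisions are made before unblinding and minuted.
- **Cases lost.** It is tempting to say that only non-cases are removed. That is wrong: someone who deviates on Day 120 and recurs on Day 200 is dropped together with the event.
- **Likelihood.** Criterion 11 already excludes anyone who plans to take another investigational product, and protocol 3.6.4 has participants reminded at every contact to report plans to join another study. At 5% per year about 39 of 810 would be excluded. Nothing in the documents supports a rate that high, or a difference between blinded arms.
- **Visibility.** PP exclusions are tabulated by arm and reason in Table 14.1.1.4, so an imbalance would show.

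These points limit the size but do not remove the problem. Review before unblinding hides the arm, but the documents do not say that it hides recurrence status. The route is also a working one: the same table shell has a row for prohibited medication, and Appendix D makes investigational treatment prohibited through Visit 8. Excluding for no major deviation without a cut-off is consistent with protocol 7.1, but it leaves the dependence on later events in place.

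**Conclusion.** The point holds as a minor defect in a supportive analysis. As written, SAP 3.1 lets PP membership turn on events after the PP clock has started, and participants with recurrence have less time to meet the criterion.

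The direction is an upward bias in PP incidence: at assumed rates of 1% to 10% per year, the placebo rate goes from 4.08 to at most 4.29 per 100 person-years. With equal rates in the arms the hazard ratio is unchanged. A shift in VE of about 1 to 2 points needs 5% to 10% per year in one arm and none in the other. These figures rest on assumed deviation rates, constant hazards and exclusion of every deviator.

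A reader might go further and infer that the PP estimate of VE is materially biased, or that the trial's conclusion is at risk. The documents support neither. They suggest no imbalance between arms, SAP 6.2 treats PP as supportive, and the mITT log-rank test that decides the primary objective does not use this exclusion.

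**What to change.** Add a sentence to SAP 3.1: PP membership is decided only on deviations that occur up to 14 days after the second vaccination. For criterion 11 this matches the Visit 6 end-point of the neighbouring items.

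Add a line to Table 2 for the primary endpoint: a participant with a later deviation that would otherwise have led to exclusion (criterion 11 or the open item) is censored at the date of that deviation. PP shares its Table 2 row with mITT and ITT, so the line must be marked as applying to PP only.

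The cost is two sentences and no new data, beyond carrying the deviation date into the PP derivation. The PP set becomes slightly larger. Censoring at the deviation assumes that the deviation says nothing about later recurrence risk, and the SAP should state that assumption.

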4.1 Statistical Considerations

Baseline is defined as the last assessment with available data prior to the first vaccination. No statistical tests comparing treatment groups at baseline will be performed.

Categorical data will be summarised by treatment group, using number and percentages of participants. Continuous data will be presented using the number of participants (N), mean, standard deviation (SD), median, lower quartile, upper quartile, minimum and maximum. Both the absolute values and the change from baseline will be presented, if applicable. For calculation of percentages the denominator will be the number of participants in the analysis set, unless otherwise specified.

Descriptive statistics for all endpoints will be presented by treatment group and Visit (if applicable) using observed cases, i.e., no imputation of missing data will be performed. Missing data for time to event endpoints is handled using censoring.

All presentations will at least be by treatment group.

For summaries presented by visit, scheduled time will be used, and trial visits will be labeled as below:

Visit	Label
3	Visit 3 (Day 0) - Baseline
4	Visit 4 (Day 14)
5	Visit 5 (Day 56)
6	Visit 6 (Day 70)
7	Visit 7 (Day 238)
8	Visit 8 (Day 421)

The following labels will be used in tables, figures, and listings:

Treatment	Label
H56:IC31: 5 µg H56/500 nmol IC31	H56:IC31
Placebo	Placebo

All will be presented in UK English.

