2.1.2.1 Key Secondary Endpoints

- Solicited adverse events and all adverse events occurring the first 14 days after each of the 1st and 2nd vaccinations
- Serious adverse events including medically important events occurring after the 1st vaccination through the end of the study

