2.2.1 Sample Size Considerations

The sample size for this trial was based on the following assumptions:

1. Estimated TB Disease Recurrence rate in placebo group: 4%/year.
2. Follow-up period for each participant: 12 Months post Day 70.
3. Drop-out/loss to follow-up rate: 10%.
4. Vaccine Efficacy (VE): 60%.
5. Type I error rate: 20% (2-sided).

Sponsor: SSI & IAVI

Vaccine: H56:IC31

Trial: POR A-055

Date: 15 SEP 2023

Version: Final 2.0

Statistical Analysis Plan

Based on the above assumptions, a sample size of 900 participants (N=450 in each treatment arm) is expected to provide the 23 TB Disease Recurrence endpoints per active versus placebo comparison required to detect with 80% power a vaccine efficacy (VE) of 60%, assuming a 10% drop-out rate (i.e., 10% excluding participants who discontinue due to TB) and 12-month post Day 70 follow-up period for each participant.

3 Analysis Populations

The following 6 analysis sets are defined in the protocol and will be used in the analyses of the data:

- Safety analysis set: The safety analysis set will consist of all participants who received at least one dose of investigational product. Participants will be evaluated according to vaccination actually received. The safety analysis set will be used for evaluation of endpoints related to safety.
- Modified intention-to-treat (mITT) analysis set: The mITT will include all randomised participants except those with TB disease recurrence before Visit 6, Day 70 (or 14 days after the 2nd dose for those who received both vaccinations). Participants will be evaluated as randomised. The mITT is the primary analysis set for the primary and secondary efficacy endpoints.
- Second modified intention-to-treat (mITT2) analysis set: The mITT2 will include all randomised participants except those with TB disease recurrence prior to 30 days after the 1st dose. Participants will be evaluated as randomised. The mITT2 is the analysis set for the 3rd exploratory efficacy endpoint (section 6.5).

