7.2 Analysis and Presentation of Safety Endpoints

7.2.1 Adverse Events

AEs will be regarded as treatment emergent AEs (TEAEs) if they occur after the 1st vaccination.

The collection periods for AEs are shown in the below table:

Table 3: Collection of AEs

Type of Event	Collection Period
Unsolicited adverse events (non-serious)	First 14 days after each vaccination (spontaneous adverse events, if any) Diary review and interview at study visit 14 days after each vaccination.
Solicited adverse events	First 7 days after each vaccination (solicited adverse events recorded daily in diary card) Diary review and interview at study visit 14 days after each vaccination.
Adverse events of special interest	Entire post-vaccination study period (i.e., 421 days).
Serious adverse events including medically important adverse events	Entire post-vaccination study period (i.e., 421 days).

Solicited adverse events are defined as events occurring within 7 days after a vaccination and of the following types:

- the injection site reactions *redness, swelling, and tenderness/pain*
- the systemic adverse events *fever* (i.e., events with PT *pyrexia* also named temperature reactions), *arthralgia, myalgia, fatigue, headache, rash, chills, and nausea*.

Solicited injection site reactions will be considered related to the IMP regardless of the causality assessment by the investigator. Therefore, related events consist of both solicited events and investigator-defined related events. Related AEs are defined as adverse reactions (ARs).

Presentations of serious adverse events (SAEs) will include medically important AEs.

An overall summary table of treatment emergent AEs by treatment will be made. The overall summary table will include number of events, number of participants, and proportion of participants in the safety analysis set reporting TEAEs (including solicited AEs), solicited AEs, AESIs, Treatment emergent SAEs, Fatal SAEs, related AEs, related SAEs, suspected unexpected SARs (SUSAR), AEs leading to discontinuation of IMP, AEs leading to discontinuation of trial, TEAEs by severity, and TEAEs by outcome. The same will be repeated for AEs occurring within 14 days after vaccination, SAEs, AESIs, solicited AEs and solicited SAEs occurring within the 7 days after each vaccination, and unsolicited AEs and SAEs occurring within the first 14 days after each vaccination.

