7.2.2 Other Safety Assessments

Injection site reactions

Injection site reactions (*redness, swelling, tenderness/pain, and other* as judged by the investigator) and axillary lymphadenopathy, defined as Lowest Level Term Lymphadenopathy axillary, on the same day as a vaccination as well as all injection site reactions after latest vaccination will be presented as follows:

- The number and percentage of participants as well as number of events will be summarised by treatment group and by vaccination (starting after 1st and after 2nd vaccination).
- The maximum size of the redness and swelling on the same day as a vaccination and in total within 7 days after latest vaccination will be summarised by treatment group and by vaccination.
- Injection site reactions will be listed including type and maximum diameter in mm and onset relative to the two vaccinations.

Temperature reactions (pyrexia)

Temperature reactions are events with PT *Pyrexia*. The maximum temperature could be recorded in the CRF. The maximum temperatures will be summarised by treatment group and vaccination (1st and 2nd). A listing will be made for all systemic reactions including pyrexia with maximum temperature if available.

Vital Signs

Vital signs (systolic and diastolic blood pressure, pulse, and axillary temperature) will be measured at each visit from 2nd screening visit (Visit 2) to Visit 6 (Day 70), and at ET visit. At Visits 3 and 5, the measurements are taken both pre-vaccination and one-hour post-vaccination.

Vital signs will be summarised by visit, including change from pre-vaccination to post-vaccination within Visit 3 and 5, respectively. For each visit it will be flagged whether there are any abnormal clinically significant vital signs. All information will be listed.

Height, Weight, and BMI

Weight is measured at all onsite visits from 1st screening visit (Visit 1) and onwards. Weight will be summarised by treatment and visit, including change from baseline, (Visit 3, Day 0) to subsequent visits. Height is measured at 1st screening visit (Visit 1) and BMI will be calculated for that visit. Height and BMI will be summarised by treatment, see section 4.3. All information will be listed. Furthermore, a box plot will present weight by visit and treatment.

Physical Examination

A complete physical examination is performed at 2nd screening visit (Visit 2). Symptom directed physical examination is performed at the two vaccination visits, Visit 3 and Visit 5. Each body system

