Tenderness/pain	xx (xx.x) xx	xx (xx.x) xx
Other	xx (xx.x) xx	xx (xx.x) xx
Axillary lymphadenopathy	xx (xx.x) xx	xx (xx.x) xx
Day 56: 2nd vaccination		
Redness	xx (xx.x) xx	xx (xx.x) xx
Swelling	xx (xx.x) xx	xx (xx.x) xx
Tenderness/pain	xx (xx.x) xx	xx (xx.x) xx
Other	xx (xx.x) xx	xx (xx.x) xx
Axillary lymphadenopathy	xx (xx.x) xx	xx (xx.x) xx
Day 1 to 7 after 2nd vaccination		
Redness	xx (xx.x) xx	xx (xx.x) xx
Swelling	xx (xx.x) xx	xx (xx.x) xx
Tenderness/pain	xx (xx.x) xx	xx (xx.x) xx
Other	xx (xx.x) xx	xx (xx.x) xx
Axillary lymphadenopathy	xx (xx.x) xx	xx (xx.x) xx
Day 8 to 14 after 2nd vaccination		
Redness	xx (xx.x) xx	xx (xx.x) xx
Swelling	xx (xx.x) xx	xx (xx.x) xx
Tenderness/pain	xx (xx.x) xx	xx (xx.x) xx
Other	xx (xx.x) xx	xx (xx.x) xx
Axillary lymphadenopathy	xx (xx.x) xx	xx (xx.x) xx

Page 1 of x

N: Number of participants, %: Percentage of participants

Trial: <Trial id>

Program: <program_name>.sas - output: <output_name>.rtf - executed: DDMMYYYY

Table 14.3.2.2: Summary of solicited injection site reactions within 7 days after vaccination – safety analysis set

<Layout similar to table 14.3.1.1>

Table 14.3.2.3: Maximum diameter of redness (mm) within 7 days after vaccination – safety analysis set

	H56:IC31	Placebo
Safety analysis set (N)	xxx	xxx
Max diameter of redness (mm)		
Day 0: 1st vaccination		
E	xx	xx
Mean (SD)	xxx.x (xx.x)	xxx.x (xx.x)
Median	xxx.x	xxx.x
q25 - q75	xxx.x - xxx.x	xxx.x - xxx.x
Min - Max	xxx - xxx	xxx - xxx
Day 1 to 7 after 1st vaccination		
E	xx	x
Mean (SD)	xxx.x (xx.x)	xxx.x (xx.x)
Median	xxx.x	xxx.x
q25 - q75	xxx.x - xxx.x	xxx.x - xxx.x
Min - Max	xxx - xxx	xxx - xxx
Day 56: 2nd vaccination		
E	xx	xx
Mean (SD)	xxx.x (xx.x)	xxx.x (xx.x)
Median	xxx.x	xxx.x
q25 - q75	xxx.x - xxx.x	xxx.x - xxx.x
Min - Max	xxx - xxx	xxx - xxx
Day 1 to 7 after 2nd vaccination		
E	xx	xx
Mean (SD)	xxx.x (xx.x)	xxx.x (xx.x)
Median	xxx.x	xxx.x
q25 - q75	xxx.x - xxx.x	xxx.x - xxx.x
Min - Max	xxx - xxx	xxx - xxx

Page 1 of x

E: Number of reactions with non-missing measurement of size.

SD: Standard deviation, q25: Lower quartile, q75: Upper quartile

Trial: <Trial id>

Program: <program_name>.sas - output: <output_name>.rtf - executed: DDMMMYYYY

Table 14.3.2.4: Maximum diameter of size of swelling (mm) within 7 days after vaccination – safety analysis set

<Layout similar to table 14.3.2.3>

Table 14.3.2.5: Summary of solicited systemic reactions within 7 days after vaccination – safety analysis set

<Layout similar to table 14.3.1.1>

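### In shell 14.3.2.1 the post-dose-2 injection-site percentages divide by everyone given at least one dose, and no table gives the frequency or severity of solicited systemic reactions by dose

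*SAP*

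**What the plan says.** **Denominator.** The default in SAP 4.1 is: "For calculation of percentages the denominator will be the number of participants in the analysis set, unless otherwise specified". SAP section 3 defines the set used for safety: "The safety analysis set will consist of all participants who received at least one dose of investigational product". For injection-site reactions and axillary lymphadenopathy, SAP 7.2.2 states: "The number and percentage of participants as well as number of events will be summarised by treatment group and by vaccination". It gives no other base for the second vaccination.

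Shell 14.3.2.1 has a single row for the safety-set N, followed by six periods. Three follow the first vaccination. The other three begin with the row block "Day 56: 2nd vaccination" and continue with days 1 to 7 and days 8 to 14 after it. There is no row for the number who received dose 2.

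**Systemic reactions.** Protocol 2.1.2.1 words the key secondary endpoint as: "Solicited adverse events and all adverse events occurring the first 14 days after each of the 1st and 2nd vaccinations". The frequency table for systemic events is 14.3.2.5, titled "Summary of solicited systemic reactions within 7 days after vaccination". It borrows the layout of 14.3.1.1, which has no split by dose. Table 14.3.1.4 (by SOC and preferred term) also pools the doses, and SAP 7.2.1 names no dose split for the systemic plot by preferred term and maximum severity. Two outputs do separate the doses: maximum temperature (SAP 7.2.2, Table 14.3.2.6) and the participant listing 16.2.7.3, which shows onset relative to each injection.

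**The concern.** A participant who did not receive dose 2 cannot have a reaction to it. Keeping that participant in the denominator turns a rate among recipients into a smaller number that the table does not explain. Missed second doses are foreseen: SAP 3.1 lists them as a major deviation, SAP Table 1 sets a start-timepoint for them, and Table 14.1.3.5 counts participants with one and with two vaccinations.

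Safety is the key secondary objective, and tolerability of the second dose is something a reader will look up directly in 14.3.2.1. For fatigue, myalgia, headache and the other systemic symptoms, the pooled tables cannot show whether reactions rise or fall at the second dose.

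**Working it through.** **The plan's own figure.** The documents state no reactogenicity rate and no share missing dose 2. The only related planning figure is the 10% drop-out in SAP 2.2.1, which enters the event count as one flat multiplier:

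450 × 0.90 × (0.04 + 0.04 × 0.40) = 405 × 0.056 = 22.68, which rounds to the stated 23.

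The figure reproduces, but it says nothing about when drop-out occurs or how many participants reach dose 2.

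**Which denominator applies.** The SAP names a different base where it wants one. SAP 4.2 uses total withdrawn for reasons for early termination, SAP 3.1 uses all randomised for exclusions from the per-protocol set, and shell 14.1.1.3 uses those not eligible. SAP 7.2.2 and shell 14.3.2.1 name none, so the default governs.

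**Formula.** Let p be the share of dose-2 recipients with a given reaction, N the safety set in an arm, and m the share of N without dose 2.

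- Count of reactors = p × N × (1 − m)
- Printed percentage = count / N = p × (1 − m)

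The relative understatement equals m.

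**Numbers.** Assume all 450 planned per arm are dosed once. The true rate of 40% is chosen for illustration only.

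| Assumption about the planned 10% | m | Receive dose 2 | Printed when p = 40% |
|---|---|---|---|
| Spread evenly, Day 56 of 421 | 10% × 56/421 = 1.33% | 444 | 40% × 0.9867 = 39.5% |
| Half lost before dose 2 | 5% | 427.5 | 40% × 0.95 = 38.0% |
| All lost before dose 2 | 10% | 405 | 40% × 0.90 = 36.0% |

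Dividing by dose-2 recipients gives 40% in every row.

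**Between arms.** With the same m in both arms, the ratio of vaccine to placebo percentages is unchanged and the difference shrinks by (1 − m). With different shares, the printed ratio is the true ratio × (1 − m_vaccine)/(1 − m_placebo). If one arm had m = 10% and the other 1.33%, the multiplier would be 0.90/0.9867 = 0.912 or 0.9867/0.90 = 1.096, depending on which arm lost more. The documents do not say which.

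**Reach of the defect.** Table 14.3.2.1 is the only reaction table with percentages by dose. The size tables 14.3.2.3 and 14.3.2.4, and the temperature table that follows their layout, summarise measured reactions and print no percentages of participants. In tables pooling both doses, everyone in the safety set could have had an event, so that denominator is right.

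**The case against.** The defence is substantial. Table 14.1.3.5 prints the number with two vaccinations by arm, for the same safety set, and 14.3.2.1 prints the counts, so the correct rate is one division away. No test or decision uses these percentages. Under even drop-out the effect is about half a point on 40%. SAP 4.1 also says descriptive statistics use observed cases, which leaves the intended handling a little less settled, though it does not displace the percentage rule. On systemic events, the endpoint wording can be read as a collection window, Protocol 7.4.6 plans no summary by dose, and the by-time-point display in Protocol 7.4.7 concerns injection-site reactions, which the SAP delivers.

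This limits the size and urgency of the point. It does not make the printed dose-2 percentages right. Nor does Table 14.1.3.5 help with systemic reactions, where a reader would have to count from a listing.

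A reader might also infer more than the documents support:

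- **That every dose-2 percentage is affected.** Only those in Table 14.3.2.1 are.
- **That systemic reactions are never shown by dose.** Maximum temperature is tabulated by dose, and onset is listed.
- **That the bias favours the vaccine.** Protocol 6.1 does stop further product for severe related changes, allergic reactions and related extensive rash, and the placebo is saline. But Protocol 1.4 describes the common earlier reactions as mild to moderate. The same rules also include active TB, which would remove more placebo participants if the vaccine works, and pregnancy and HIV seroconversion, which have no stated direction by arm. A differential is possible; its net direction is not established.

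**Conclusion.** The point holds in a narrow form. If the SAP is followed as written, the injection-site and axillary lymphadenopathy percentages for the three dose-2 periods of Table 14.3.2.1 are understated by the factor (1 − m). On the planning figure alone this runs from about 1.3% relative (40% prints as about 39.5%) to 10% relative (40% prints as 36.0%). Both values of m are assumptions, and 10% is not a ceiling, because a participant can miss dose 2 and stay in the trial. The arithmetic holds for any m; the actual size will be known only from the data.

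Separately, no table gives the frequency or severity of solicited systemic reactions by dose, although the endpoint refers to each vaccination. This is a gap in presentation. Efficacy conclusions are untouched.

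**What to change.** In SAP 7.2.2 and shell 14.3.2.1, add a row by arm for the number receiving the second vaccination, and state that it is the denominator for the three dose-2 periods. SAP 4.1 needs no change, because its default already gives way to a specified exception.

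In Table 14.3.2.5, and in 14.3.1.4 if wanted, add blocks for after dose 1 and after dose 2, each with its own N, beside the pooled figures. The pooled any-dose tables keep the safety-set denominator. Splitting the unsolicited and remaining SOC/PT tables by dose is a matter of preference and is not needed for this point.

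The cost is minor shell wording and programming. No new data are required: vaccination dates are recorded, and listings 16.2.7.2 and 16.2.7.3 already show onset relative to each injection.
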